## 2.2.2 Rationale for Acalabrutinib in AIHA

Second-line therapy of AIHA with cytotoxic and immunosuppressive drugs such as azathioprine, cyclophosphamide, and cyclosporine is reported to provide a 40%-60% response rate, but their use is often associated with serious side effects. Anti-CD20 targeting with rituximab for the treatment of

relapsed/refractory AIHA achieves a 60-70% response rate, with a median duration of response of 19 months. However, most of these patients inevitably relapse. Although splenectomy remains an option in this setting, surgical morbidity and risk for serious infectious complications are inherent challenges to this treatment approach. Likewise, other treatment options such as plasmapheresis, and danazol have not proved effective. Altogether, these findings highlight the need for novel treatment approaches, especially in CLL-associated AIHA where there is little prospective or retrospective data on these approaches and immunosuppression will have higher risks due to the already increased risk for infection in patients with CLL.

Preclinical and preliminary clinical evidence strongly suggests that BTK inhibition modulates the immune system and may be efficacious in the treatment CLL-associated AIHA. A second generation BTK inhibitor, acalabrutinib, provides a novel approach to evaluate the impact of BTK inhibition on treating AIHA, as well as control the underlying autoimmune or lymphoproliferative disorder that may be driving AIHA. Moreover, acalabrutinib has gained increasing favor as a second-generation BTK inhibitor with potentially fewer off-target effects leading to side effects such as bleeding and atrial fibrillation. This makes acalabrutinib an attractive option for treatment of AIHA. The aim of this study is to investigate whether acalabrutinib will be effective in the treatment of relapse or refractory AIHA, and assess its effect on T-cell function in patients with CLL.

### **2.3 Background for Correlative Studies**

Recent data suggests that ibrutinib increased CD4 and CD8 T-cell numbers, resulting in an increased Tcon/Treg ratio in CLL patients, but this effect was not observed with acalabrutinib. However, both ibrutinib and acalabrutinib reduced expression of PD-1 and CTLA-4, suggesting that an immunolodulatory effect may still be observed with acalabrutinib. Thus, this study will evaluate the effects of acalabrutinib on T-cell populations. Particularly, these in vitro studies will measure T-cell activation across participant samples pre-acalabrutinib, then 3 and 6 months after initiating therapy with acalabrutinib.

### **2.4 Overview and Rationale of Study Design**

Refer to [Section 12.0 Statistical Considerations](#) for additional information regarding statistical methods used in this study.

This is a single-arm, open label, phase II study to assess the efficacy of acalabrutinib in controlling relapsed or refractory AIHA in a setting of CLL. Participants must meet the inclusion criteria, have none of the exclusion criteria, and have provided written informed consent before the conduct of any screening tests not performed routinely in their treatment.

In this study, eligible participants will have a diagnosis of wAIHA or CAD (cold agglutinin disease) who had a recurrence, did not respond to, or did not tolerate at least one prior AIHA treatment with corticosteroid. Eligible participants will be administered acalabrutinib (100 mg PO BID) daily for 12 cycles (each cycle is 28 days). Treatment with acalabrutinib may be continued beyond 12 cycles if the study participant might benefit from ongoing therapy in the opinion of treating physician (e.g., ongoing therapy for CLL is required); the maximum number of cycles allowed on this study in such situations is 36 cycles. At the end of this treatment period (i.e. after acalabrutinib is discontinued), participants will be considered off-treatment and undergo follow-up evaluations in accordance with institutional standards (refer to [Section10.0 Study Calendar](#)).

A total of 22 participants are planned for enrollment to this study over a period of 36 months. After 6 patients are enrolled on study, investigators will discuss whether it is reasonable to continue accrual based on overall drug safety profile seen in the first 6 patients. Further enrollment will be held if two or more patients (of the first 6 patients) develop any grade 4 toxicity (assessed as possibly, probably, or definitely related to study drug) during cycle 1 of treatment, or if ≥3/6 patients need to discontinue therapy with acalabrutinib during cycle 1 of treatment due to perceived lack of efficacy. Accrual will also be paused any time if any death possibly, probably, or definitely attributed to study treatment occurred.

### 3.0 ELIGIBILITY CRITERIA

Patient MRN (COH Only)	Patient Initials (F, M, L):
Institution:	

Participants must meet all of the following criteria on screening examination to be eligible to participate in the study:

#### 3.1 Inclusion Criteria

##### Informed Consent and Willingness to Participate

\_\_\_1. Documented informed consent of the participant and/or legally authorized representative.

- Assent, when appropriate, will be obtained per institutional guidelines

##### Age Criteria, Performance status

\_\_\_2. Age:  $\geq 18$  years

\_\_\_3. ECOG  $\leq 2$

##### Nature of Illness and Illness Related Criteria

\_\_\_4. "Warm" or "cold" AIHA in patients with CLL, relapsed/refractory (RR) after first line treatment with oral prednisone (with or without rituximab), defined as:

- anemia ( $Hgb \leq 10$  g/dL; or  $Hgb > 10$  g/dL dependent on transfusions or maintenance therapy (rituximab, cyclosporin, etc) to maintain this level of hemoglobin, and
- laboratory evidence of hemolysis – presence of 3 of 4 markers (increased reticulocyte count, increased indirect bilirubin, increased lactate dehydrogenase, absent haptoglobin)

\_\_\_5. Positive DAT (score  $\geq 1+$ ) – either IgG DAT, C3 DAT, or both. Eligibility of patients with Coombs-negative AIHA should be confirmed by the trial investigator at each respective study site.

\_\_\_6. Histologically or flow cytometry confirmed diagnosis of CLL/SLL

\_\_\_7. Participant must be able to swallow tablets or capsules.

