### 3.2 Exclusion Criteria

#### Prior and concomitant therapies

- \_\_\_ 1. therapeutic anticancer antibodies within 2 weeks;
- \_\_\_ 2. radio- or toxin-immunoconjugates within 10 weeks;
- \_\_\_ 3. BH3-mimetic venetoclax, PI3K inhibitors and other “targeted” therapy– within 6 half-lives;
- \_\_\_ 4. Ibrutinib, acalabrutinib or another BTK inhibitor within 12 months
- \_\_\_ 5. Patients on stable chronic AIHA treatments are allowed provided the dose has not changed in the 4 weeks prior to enrollment
- \_\_\_ 6. Allogeneic stem cell transplant within 1 year prior to Day 1 of protocol therapy, or ongoing immunosuppressive therapy for cGVHD
- \_\_\_ 7. Chemotherapy, radiation therapy, biological therapy, immunotherapy within 21 days prior to Day 1 of protocol therapy

\_\_8. Strong CYP3A4 inducers/ inhibitors. If the patient requires a strong CYP3A inhibitor/inducer, they should not be enrolled even if it could be held for 14 days before the first dose of study drug.

\_\_9. Proton pump inhibitors (but patients who switch to H2-receptor antagonists or antacids are eligible for enrollment).

\_\_10. Chronic use of corticosteroids (>2 weeks) in excess of prednisone 60 mg/day or its equivalent within 4 weeks prior to start of study therapy. Rescue steroids are allowed during trial.

\_\_11. Vitamin K antagonists

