## 11.0 ENDPOINT DEFINITIONS/MEASUREMENT OF EFFECT

### 11.1 Primary Endpoint(s)

Objective	Endpoint	Start	End
Assess the efficacy of acalabrutinib in CLL patients with relapsed or refractory AIHA	AIHA ORR after 6 cycles [ORR defined as proportion of patients who achieve complete and partial response; refer to Appendix B ]	First dose of study drug [i.e. C1 Day 1]	After 6 cycles of therapy

Primary endpoint of AIHA ORR after 6 cycles will be defined as the proportion of patients achieving AIHA complete or partial response after 6 cycles. Patients evaluable for this endpoint include: 1) those who receive at least 6 cycles of treatment and have AIHA response evaluation after 6 cycles (each cycle = 28 days); 2) patients who terminate acalabrutinib prior to completing 6 cycles due to AIHA or CLL progressive disease (they will be counted as non-responders).

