**APPENDIX B: AIHA RESPONSE CRITERIA**

Treatment response will be determined per the investigators' assessment, according to Barcellini et al.

AIHA Complete Response (CRAIHA):	Hemoglobin >12 g/dL, AND no transfusion requirements. No laboratory evidence of ongoing hemolysis (haptoglobin, indirect bilirubin WNL, reticulocyte count <1.5 ULN)
AIHA Partial Response (PRAIHA):	Hemoglobin level ≥10 g/dL (without transfusions), OR hemoglobin increase of at least 2 g/dL above pretreatment level, Presence of laboratory evidence of ongoing hemolysis.

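### Some patients can enter already meeting the Appendix B partial response, and the 30% no-benefit benchmark does not fit them

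*Combined protocol and SAP*

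**What the plan says.** **Entry.** Inclusion 4 in Section 3.1 accepts hemoglobin of 10 g/dL or less. It also accepts a higher value if the patient is "dependent on transfusions or maintenance therapy (rituximab, cyclosporin, etc) to maintain this level of hemoglobin". Both routes also need laboratory hemolysis, defined as "presence of 3 of 4 markers (increased reticulocyte count, increased indirect bilirubin, increased lactate dehydrogenase, absent haptoglobin"). The synopsis version of this criterion lists transfusion dependence only and has no maintenance-therapy route.

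**Background treatment.** Section 3.2, item 5 states: "Patients on stable chronic AIHA treatments are allowed provided the dose has not changed in the 4 weeks prior to enrollment".

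**Response.** Appendix B defines partial response by "Hemoglobin level ≥10 g/dL (without transfusions") or, alternatively, "hemoglobin increase of at least 2 g/dL above pretreatment level", together with "Presence of laboratory evidence of ongoing hemolysis".

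**Primary endpoint.** Section 11.1 uses the "proportion of patients achieving AIHA complete or partial response after 6 cycles". The evaluable set is "those who receive at least 6 cycles of treatment and have AIHA response evaluation after 6 cycles", plus patients who stop earlier for AIHA or CLL progression, who count as non-responders.

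**Test.** Section 12.2 sets a one-sided exact binomial test of 30% against 60%. It rejects at 10 or more responders among 20 evaluable patients, with type I error 0.048 and power of about 87%.

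**The concern.** The two hemoglobin limbs of partial response are joined by OR, so the 10 g/dL limb is absolute. Take an untransfused patient who enters at 10.8 g/dL on stable maintenance with three hemolysis markers. Every element of partial response is met at screening. If nothing changes over six cycles, this patient is a primary responder. An untransfused patient at exactly 10.0 g/dL is in the same position, since 10.0 satisfies both the entry limit and the response limit.

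The primary objective is the efficacy of acalabrutinib. For these patients the endpoint can be met by persistence of the entry state, possibly under another drug, and a single-arm trial has no control group to reveal this. The result turns on 10 versus 9 responders of 20, so a few such patients can decide it.

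**Working it through.** **1. Entry and response side by side, for an untransfused patient on maintenance therapy**

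| Element | Inclusion 4 | Appendix B partial response |
|---|---|---|
| Hemoglobin | above 10 g/dL | at least 10 g/dL |
| Transfusion | not needed on the maintenance route | none |
| Hemolysis | 3 of 4 markers required | present |
| Change from baseline | not applicable | not required (OR) |

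Every response element is met at entry. Transfusion-dependent patients are not affected, because the 10 g/dL limb excludes transfusion. Sections 11.1, 12.2.1, 12.4.1 and 12.5 contain no rule that excludes, reclassifies or separately reports patients in partial response at baseline.

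**2. How far other sections narrow the route**

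- Rituximab, named in inclusion 4, is prohibited during screening and participation (Section 5.9.2).
- Cyclosporine, also named, is listed as a moderate CYP3A inhibitor to be avoided (Section 5.9.3, Table 5.9.1), while Table 7.2.2 provides for co-administration with moderate inhibitors.
- Corticosteroids are expected to be tapered to 20 mg/day or less by week 8 (Section 5.10.1). That is 24 − 8 = 16 weeks before the end of six 28-day cycles.

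What remains is unchanged low-dose steroid, other permitted stable AIHA treatment (Section 3.2, item 5), and carry-over from earlier therapy.

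**3. The plan's own figures reproduce**

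- P(Bin(20, 0.30) ≥ 10) = 0.04796, stated as 0.048.
- P(Bin(20, 0.60) ≥ 10) = 0.8725, stated as about 87%.
- A cut-off of 9 would give 0.113, so 10 is the correct boundary.

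**4. Effect of k patients already in partial response at entry**

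Assume that k of the 20 evaluable patients are in partial response at entry and that each keeps it with probability q. The other 20 − k respond at 0.30. Then

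P(≥10) = Σⱼ P(Bin(k, q) = j) × P(Bin(20 − k, 0.30) ≥ 10 − j), for j = 0 to k.

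For k = 1 and q = 1 this is P(Bin(19, 0.30) ≥ 9) = 0.084.

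| k | q = 1.0 | q = 0.8 | q = 0.6 |
|---|---|---|---|
| 0 | 0.048 | 0.048 | 0.048 |
| 1 | 0.084 | 0.074 | 0.063 |
| 2 | 0.141 | 0.110 | 0.083 |
| 3 | 0.225 | 0.159 | 0.106 |
| 4 | 0.340 | 0.223 | 0.135 |

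The mean response rate at q = 1 is (k + 0.30 × (20 − k))/20. That is 33.5%, 37%, 40.5% and 44% for k = 1 to 4.

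**5. Power cost of a stricter rule**

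Assume that the k patients, now judged by complete response or a 2 g/dL rise, respond at 0.3 while the others respond at 0.6. The same formula gives power 0.809 for k = 2 and 0.727 for k = 4, against 0.872 for k = 0. At an assumed 0.2 the values are 0.786 and 0.667.

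**The case against.** Four points can be made for the plan.

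- **The route is narrower than inclusion 4 suggests.** This stands. A reader might infer that every maintenance-route patient is a near-certain responder. The documents do not support that: rituximab is barred on study, cyclosporine is to be avoided, and higher-dose steroids are expected to fall. A patient who holds 10 g/dL after treatment is withdrawn or reduced may be showing a real effect. But Appendix B does not make response depend on withdrawal, so the endpoint cannot tell that patient from one in whom nothing changed.
- **The test keeps its size.** This also stands. A reader might infer that the 0.048 is wrong. It is correct for a true rate of 30%. With k such patients the true rate of the defined endpoint is above 30%, so the statistical null is false even if the drug does nothing. The fault lies in 30% as the no-benefit benchmark for this mix.
- **Few patients may qualify.** They must be relapsed or refractory, untransfused, at or above 10 g/dL and hemolyzing. This is fair, and k is unknown. One such patient still takes the probability above 0.05 in every scenario shown. The exact 10.0 g/dL overlap is a single-value tie and adds little.
- **A stricter rule has its own defects.** A patient at 9.9 g/dL needs a rise of 0.1 while one at 10.0 needs 2 g/dL, and some power is lost. Both are true. They are reasons to report the affected patients openly and keep the current rule as a sensitivity analysis.

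**Conclusion.** The overlap is real on the text as written. An untransfused patient at or above 10 g/dL with the required hemolysis can meet partial response before treatment and be counted as a primary responder without any change. For such patients the 30% benchmark does not represent absence of benefit.

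If acalabrutinib added nothing, the probability of declaring the trial promising with one to four such patients would be 0.084 to 0.340 under full retention, 0.074 to 0.223 at 80% retention, and 0.063 to 0.135 at 60%. These figures rest on assumed values of k and q, neither of which is in the documents, and on a 30% rate in everyone else. The finding rests on Appendix B as printed; the publication it cites was not consulted.

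**What to change.** 1. Reconcile the anemia criterion in the synopsis (transfusion route only) with inclusion 4 (transfusion or maintenance route). Reconcile inclusion 4 with Section 5.9.2, Section 5.9.3, Table 5.9.1 and Table 7.2.2 on the maintenance drugs it names.
2. Add to Section 11.1 and Appendix B: *A patient who already meets the partial response criteria at baseline (untransfused C1D1 hemoglobin of 10 g/dL or more) is a primary responder only by complete response or by a hemoglobin rise of at least 2 g/dL over baseline.* Define the look-back window that makes a C1D1 value untransfused.
3. Report the number of such patients with the primary result, and give a sensitivity analysis under the Appendix B rule as it now stands.

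**Cost.** A few sentences of text. C1D1 hemoglobin and baseline transfusion requirements are already collected (Section 10.0), so visits and data collection do not change. The price is that a patient who holds hemoglobin after coming off maintenance is not credited in the primary analysis. With two such patients responding at an assumed 0.3, power falls from 0.872 to 0.809. Describe these patients separately.

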##### Clinical Laboratory and Organ Function Criteria (To be performed within 30 days prior to Day 1 of protocol therapy unless otherwise stated)

___8. ANC $\geq 500/\text{mm}^3$ unless due to disease involvement in the bone marrow or autoimmune neutropenia.	ANC:	Date:
___9. Platelets $\geq 30,000/\text{mm}^3$ unless due to disease involvement in the bone marrow or autoimmune thrombocytopenia (Evans syndrome).	Plts:	Date:
___10. Direct bilirubin $\leq 3.0 \times \text{ULN}$ , or 1 mg/dL, whichever is higher, if deemed related to hemolysis by the investigator.	ULN: Bil:	Date:
___11. AST $\leq 3.0 \times \text{ULN}$	ULN: AST:	Date:
___12. ALT $\leq 3.0 \times \text{ULN}$	ULN: ALT:	Date:

___ 13. Creatinine clearance of <math>\geq</math> 30 mL/min per 24 hour urine test or the Cockcroft-Gault formula or
 $\text{CrCl} \text{ (mL/min)} = \frac{(140-\text{age}) \times \text{actual body weight (kg)}}{72 \times \text{serum creatinine (mg/dL)}} \text{ (} \times 0.85 \text{ for females)}$ 
Or
 $\text{CrCl} \text{ (mL/min)} = \frac{(140-\text{age}) \times \text{actual body weight (kg)}}{0.8136 \times \text{serum creatinine (umol/L)}} \text{ (} \times 0.85 \text{ for females)}$	
Serum Cr:
 
Cr Clearance:
	Date:

___ 14. If not receiving anticoagulants: International Normalized Ratio (INR) OR Prothrombin (PT) <math>< 2 \times</math> ULN  If on anticoagulant therapy: PT must be within therapeutic range of intended use of anticoagulants
	
ULN:  INR:  PT:
	Date:

___ 15. If not receiving anticoagulants: Activated Partial Thromboplastin Time (aPTT) <math>< 2 \times</math> ULN  If on anticoagulant therapy: aPTT must be within therapeutic range of intended use of anticoagulants
	
ULN:  aPTT:
	Date:

___ 16. Seronegative for HIV Ag/Ab combo, HCV*, active HBV (Surface Antigen Negative), and syphilis (RPR)  *If positive, Hepatitis C RNA quantitation must be performed.
	
HIV:  HCV:  HBV:  Syphilis:
	Date:

___ 17. Women of childbearing potential (WOCBP): negative urine or serum pregnancy test within the screening window prior to receiving the first dose of study medication.  If the urine test is positive or cannot be confirmed as negative, a serum pregnancy test will be required
	
Urine:  Serum:
	Date:

#### Contraception

\_\_\_ 18. Agreement by females of childbearing potential to use highly effective methods of birth control or abstain from heterosexual activity starting with the first dose of study therapy through 2 days after the last dose of protocol therapy.

\* Childbearing potential defined as not being surgically sterilized (men and women) or have not been free from menses for  $> 1$  year (women only).

### 3.2 Exclusion Criteria

#### Prior and concomitant therapies

- \_\_\_ 1. therapeutic anticancer antibodies within 2 weeks;
- \_\_\_ 2. radio- or toxin-immunoconjugates within 10 weeks;
- \_\_\_ 3. BH3-mimetic venetoclax, PI3K inhibitors and other “targeted” therapy– within 6 half-lives;
- \_\_\_ 4. Ibrutinib, acalabrutinib or another BTK inhibitor within 12 months
- \_\_\_ 5. Patients on stable chronic AIHA treatments are allowed provided the dose has not changed in the 4 weeks prior to enrollment
- \_\_\_ 6. Allogeneic stem cell transplant within 1 year prior to Day 1 of protocol therapy, or ongoing immunosuppressive therapy for cGVHD
- \_\_\_ 7. Chemotherapy, radiation therapy, biological therapy, immunotherapy within 21 days prior to Day 1 of protocol therapy

\_\_8. Strong CYP3A4 inducers/ inhibitors. If the patient requires a strong CYP3A inhibitor/inducer, they should not be enrolled even if it could be held for 14 days before the first dose of study drug.

\_\_9. Proton pump inhibitors (but patients who switch to H2-receptor antagonists or antacids are eligible for enrollment).

\_\_10. Chronic use of corticosteroids (>2 weeks) in excess of prednisone 60 mg/day or its equivalent within 4 weeks prior to start of study therapy. Rescue steroids are allowed during trial.

\_\_11. Vitamin K antagonists

**Other illnesses or conditions**

\_\_12. Known intolerance to acalabrutinib

\_\_13. History of bleeding disorders or with active bleeding.

\_\_14. Patients with suspected or confirmed progressive multifocal leukoencephalopathy (PML)

\_\_15. Patients with history of stroke or intracranial hemorrhage within 6 months.

\_\_16. Inadequate recovery from adverse events related to prior therapy to grade 1 or baseline (excluding Grade 2 alopecia and neuropathy).

\_\_17. Active uncontrolled infection

\_\_18. Known history of immunodeficiency virus (HIV) infection

- Subjects who have an undetectable or unquantifiable HIV viral load with CD4 > 300 and are on HAART medication are allowed. Testing to be done only in patients suspected of having infections or exposures.

\_\_19. Active infection with hepatitis B virus (HBV) or hepatitis C virus (HCV).

- Participants who are hepatitis B core antibody (anti-HBc) positive and who are surface antigen negative will need to have a negative polymerase chain reaction (PCR). Those who are hepatitis B surface antigen (HbsAg) positive or hepatitis B PCR positive will be excluded. Note that IVIG administration may lead to positive anti-HBc test result.
- Subjects who are hepatitis C antibody positive will need to have a negative PCR result. Those who are hepatitis C PCR positive will be excluded.

\_\_20. Major surgery (requiring general anesthesia) within 28 days prior to initiation of therapy.

\_\_21. Has difficulty with or is unable to swallow oral medication, or has significant gastrointestinal disease that would limit absorption of oral medication.

\_\_22. History of prior malignancy except:

- Malignancy treated with curative intent and no known active disease present for  $\geq$  2 years prior to initiation of therapy on current study;
- Adequately treated non-melanoma skin cancer or lentigo maligna (melanoma in situ) without evidence of disease;
- Adequately treated in situ carcinomas (e.g., breast, cervical, esophageal, etc.) without evidence of disease;
- Asymptomatic prostate cancer managed with “watch and wait” strategy;

\_\_23. Significant cardiovascular disease such as uncontrolled or symptomatic arrhythmias, congestive heart failure, or myocardial infarction within 6 months of screening, or any Class 3 or 4 cardiac disease as defined by the New York Heart Association Functional Classification, or left ventricular ejection fraction (LVEF)  $\leq$  40%.

\_\_24. Psychiatric illness/social situations that would limit compliance with study requirements.

\_\_25. Participant is pregnant or breastfeeding, or expecting to conceive or father children within the projected duration of the trial.

26. Any other condition that would, in the Investigator's judgment, contraindicate the patient's participation in the clinical study due to safety concerns with clinical study procedures.

Noncompliance

27. Prospective participants who, in the opinion of the investigator, may not be able to comply with all study procedures (including compliance issues related to feasibility/logistics).

Eligibility Confirmed* by (Choose as applicable):	Print Name	Signature	Date
 Site PI			
 Authorized study MD			
 Study Nurse			
 Study CRA/ CRC			
 Other: _____			

\*Eligibility should be confirmed per institutional policies.

